#### 6.4 Blinding

This is a triple-blind trial, with trial participants, care providers and endpoint assessors to the treatment group allocation. The primary outcome will be analysed by individuals masked to the patient treatment allocation and clinical outcomes. Afferent Medical Solutions Ltd will be unblinded to facilitate reporting of Serious Adverse Device Events (SADE) or Unexpected Serious Adverse Device Events (USADEs) to the MHRA. The blinded interventions are highly comparable, as the same device will be used for all participants randomized to either active stimulation or turned off. Final unblinding of all study participants will occur after the data set is locked.

#### 6.5 Unblinding

Unblinding a participant's treatment is strongly discouraged as it can compromise the integrity of the trial. However, unblinding may be necessary on rare occasions for medical or safety reasons that can affect clinical management. In this trial, unblinding may be required if a patient experiences a cardiac arrhythmia of concern to attending clinicians. The PI or assigned delegate must determine the necessity of unblinding, and contact the study coordinating team for further discussion. Healthcare professionals will be provided with emergency contact details of the research team to quickly unblind a participant if knowledge of the treatment assignment is essential for optimal medical treatment. A 24-hour emergency unblinding procedure will be available, and participants will receive a trial card with emergency contact details. Unblinding requests are expected to be rare as the rescue treatment should not depend on the treatment group allocation.

To ensure the safe unblinding of information in case of a safety concern, we will store unblinding details in a securely locked cupboard that can be accessed by the research/clinical team with prior discussion and approval from the PI or their designated representative. The cupboard will be accessible at all times. Unblinding information will be contained in opaque sealed envelopes that will be labelled with the corresponding stimulator box number and contain treatment group allocation (stimulation or sham) inside. The Statistician will be responsible for inserting the treatment group information and sealing each envelope, which will be witnessed and verified by an independent staff member not involved in the trial. This process will ensure that the treatment group allocation cannot be viewed without opening the sealed envelope. To enhance the security and confidentiality of the unblinding process, each envelope will be signed by the Statistician on the back, and they can be examined at the end of the trial to verify that none of them have been tampered with. The envelopes will be kept in a designated folder that is labelled clearly, and this folder will be stored in a securely locked cupboard that can be accessed at any time of the day. The Statistician and the witness will sign a file note that outlines the process used to create and seal the envelopes.

Treatment identification information should be kept confidential and should be disseminated only to those individuals involved with the medical management of the participant. The Chief Investigator and Principal Investigator will be kept informed of all instances of unblinding but should remain blinded to treatment allocations themselves. The Trial Manager and the site staff will maintain a record of all unblinding events including: patient trial ID, the date code break was performed, the person who broke the blind, and reason for it. The breaking of the code and the reasons for doing so will also be captured on the electronic case report form (eCRF), in the site file and medical notes. The code break for the trial will be held by the trial coordinator until the end of the trial when it will be filed in the Trial Master File (TMF). The Chief Investigator will ensure any unblinding is documented at the end of the study in any final study report and/or statistical report. The information will also be disseminated to the Trial steering Committee (TSC).

#### 6.6 Study assessments

The following data will be collected from all patients:

Randomisation data

- Initials
- Date of consent and mechanical thrombectomy
- Age
- Sex
- Ethnicity
- Trial ID (generated automatically at the point of randomisation)

#### Baseline data

- Ethnicity
- Medical history
- Smoking status (within the last 14 days)
- Cardiovascular medications
- Laboratory values (haemoglobin, creatinine, neutrophil/lymphocyte count, albumin)
- NIHSS on admission to Royal London Hospital
- Systolic and diastolic blood pressure
- Blood sample
- Pre mechanical thrombectomy resting heart rate
- Planned level of care on the first night after mechanical thrombectomy
- Safety review

#### During mechanical thrombectomy

- Start and end times of mechanical thrombectomy
- Start and end times of TAN
- Anaesthetic technique (general anaesthesia/sedation)
- Clinically recorded arrhythmias
- Heart rate (Holter) during first intervention period
- Systolic blood pressure
- Diastolic blood pressure
- Level of care
- Safety review

#### 24 hours after the start of mechanical thrombectomy

- NIHSS
- Start and end times of TAN
- Clinically recorded arrhythmias
- Blood sample after the end of TAN stimulation period
- Cardiovascular medications
- Level of care
- Laboratory values, if available (haemoglobin, creatinine, neutrophil count, lymphocyte count, albumin)
- Heart rate (Holter) during second intervention period
- Systolic blood pressure

- Diastolic blood pressure
- Hospital discharge (if applicable)
- Safety review

#### Day seven follow-up

- Mortality status and in hospital stay seven days after mechanical thrombectomy
- Safety review

#### 6.7 Trial intervention

Each participant will have the Affex-CT device connected to both ears via electrical leads. The device will be preset to deliver either transcutaneous autonomic neuromodulation or no stimulation. In the treatment arm, the device will be turned 'On' by a trained member of the research team and the transcutaneous autonomic neuromodulation will be applied continuously until the end of the stimulation period when the device will be turned 'Off'. For the control arm, no stimulation will be applied.

The intervention will be administered across two time points in each participant. The first will be delivered for the entire duration of the mechanical thrombectomy procedure. The start of mechanical thrombectomy is defined at induction of anaesthesia which is the patient's arrival in the anaesthetic room but before being wheeled into the radiology suite. The end of mechanical thrombectomy is defined as the point the patient leaves the radiology suite to be taken to the post recovery anaesthetic room. The second will be delivered on the morning after mechanical thrombectomy regardless of the time when the first procedure was administered. This will happen typically in the morning between 0800-1200h for one hour (± 10 minutes). The duration of participation is seven days from the start of the mechanical thrombectomy procedure for each participant. No special dietary or 'life-style' requirements will be imposed (this study will gather efficacy data for the intervention while establishing the feasibility of a full-scale trial).

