# IV. Synopsis

Full title	Autonomic modulation by transcutaneous vagal nerve stimulation in acute ischaemic stroke requiring mechanical thrombectomy: a phase IIa, sham controlled randomised trial.				
Short title and / or acronym	VANS				
Sponsor	Queen Mary, University of London				
Device classification	Class IIa				
Medical condition or disease under investigation	Acute ischaemic stroke requiring mechanical thrombectomy				
Study design and methodology	Triple-blind, randomised controlled trial, single NHS -site				
Planned number of participants	36				
Objectives	To determine whether non-invasive transcutaneous autonomic neuromodulation results in lower blood pressure variability in the first 24 hours from the start of mechanical thrombectomy, as measured by coefficient of variation compared to the control treatment.				
Inclusion and exclusion criteria	Inclusion criteria:				
Investigational Device(s)	AffeX-CT/001				
Treatment duration	Approximately $1-3$ hours of treatment across two separate calendar days.				
Follow up duration	Seven days after index mechanical thrombectomy				
Total duration for participants	Four months				
Planned Enrolment Period	Six months				
End of Trial definition	When the last patient has completed their seven day follow-up				

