### 2.3 Endpoints

#### 2.3.1 Primary endpoint(s)

Coefficient of variation of systolic blood pressure measured in each patient during the first 24 hours from the start of mechanical thrombectomy.

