# 2.3.2 Secondary endpoint(s)

- Systolic blood pressure variability from blood pressure measured in each patient during the first 24 hours from the start of mechanical thrombectomy.
- Disatolic blood pressure variability from blood pressure measured in each patient during the first 24 hours from the start of mechanical thrombectomy.
- Heart rate variability measured during each period of transcutaneous autonomic neuromodulation.
- NIH Stroke Scale (NIHSS) measured in each patient before the start of mechanical thrombectomy and 24 hours after the start of procedure.
- Clinically recorded arrhythmias in each patient during the first 24 hours after the start of mechanical thrombectomy.
- Absolute levels of serum high-sensitivity troponin-T levels measured before the start of the first transcutaneous autonomic neuromodulation and at the end of the second transcutaneous autonomic neuromodulation.

[figure not shown]

\* please see Appendix A for details on the assessment of primary and secondary outcomes

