#### Visit 3 (day after mechanical thrombectomy)

- The AffeX-CT device will be applied to each ear for typically one hour during this period
- Heart rate data will be captured by dedicated Holter monitors.
- Study data will be collected including concomitant medication and NIHSS will be recorded.
- Blood samples blood will be collected after the one hour stimulation period.
- Blood pressure data will be downloaded from the electronic health record and stored securely within QMUL/Barts Health NHS Trust for subsequent analysis.

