# 10.10 Usage schedules

- First administration will be for duration of mechanical thrombectomy [which typically lasts two hours]
- Second administration will be the morning after the mechanical thrombectomy [0800-1200h] which typically lasts one hour.
- No changes to usage schedule are required for different age groups or demographics.

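### Session 2 is set for the next calendar morning, so for thrombectomies starting between midnight and 08:00 it falls after the protocol's 24-hour endpoint windows have closed

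*Protocol*

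**What the plan says.** **Timing of session 2.** Protocol section 6.7: "The second will be delivered on the morning after mechanical thrombectomy regardless of the time when the first procedure was administered". Section 10.10 gives the clock band: "Second administration will be the morning after the mechanical thrombectomy [0800-1200h] which typically lasts one hour". Section 6.7 gives the same band but calls it typical. Section 6.1 places Visit 3, with the second session, on the day after thrombectomy, and the Synopsis describes "hours of treatment across two separate calendar days".

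**Endpoint windows.** The primary endpoint (section 2.3.1) is "Coefficient of variation of systolic blood pressure measured in each patient during the first 24 hours from the start of mechanical thrombectomy", and the SAP's primary analysis also runs 24 h from the start. The other blood pressure variability measures in section 2.3.2 share that window. So does the arrhythmia endpoint: "Clinically recorded arrhythmias in each patient during the first 24 hours after the start of mechanical thrombectomy". Appendix A sets the follow-up NIHSS at 24 h from the start. Time zero is induction of anaesthesia (section 6.7, Appendix A).

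**Assumed order.** The schedule in section 6.2 puts the morning-after column before the 24-hour column. Section 6.6 lists the stimulation times, the post-stimulation blood sample and "Heart rate (Holter) during second intervention period" under the 24-hour heading.

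**Where the SAP differs.** SAP section 3 counts arrhythmias within organ dysfunction over the first seven days. Its outcome headings describe the blood pressure window as 0–24 h after thrombectomy.

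**The concern.** Thrombectomy is an emergency procedure, and no section restricts its start time. A session fixed to the next calendar morning and windows fixed to elapsed time agree only for some start times. The plan reads as if session 2 always came before the 24-hour assessment, and no section covers the reverse order. The SAP's sensitivity analysis deals with patients discharged or repatriated before the repeat session, so its authors saw that missing session 2 matters. It does not deal with patients who receive session 2 too late to affect the endpoint.

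Two things are at stake:

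- **Interpretation of the primary result.** The intervention is two sessions, but the primary endpoint reflects one or two depending on the time of day.
- **Capture of arrhythmia.** Section 1.3 names arrhythmia as a theoretical risk, and section 6.5 gives it as a reason to unblind. The protocol's arrhythmia endpoint and its listed collection points stop at 24 h, and the day-7 list in section 6.6 holds only mortality and in-hospital status plus a safety review. Section 11.3 says that an event judged not serious is not entered as an adverse event on the CRF, although the same section also says that all events go on the CRF. The SAP's seven-day frame therefore has no arrhythmia item to fill it after 24 h.

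**Working it through.** **1. The plan's own sample size.** Inputs (SAP, sample size): means 15 and 10, SD 4, 5% significance, 90% power, 5% non-compliance in each group. Diluted difference = 5 × (1 − 0.05 − 0.05) = 4.5. A two-sided two-sample t-test needs 17.6, so 18 per arm and 36 in total. The stated figure reproduces, with 90.6% power at 18 per arm. It is not in dispute.

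**2. Where session 2 falls.** Let T be the clock hour at which thrombectomy starts and S the clock hour at which session 2 starts on the next calendar day. S runs from 8 to 11, so that a one-hour session ends by 12:00. Session 2 then begins S + 24 − T hours after the start. It is

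- wholly outside a 24 h window if T ≤ S;
- straddling the close if S < T < S + 1;
- wholly inside if T ≥ S + 1.

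| Thrombectomy start | Session 2 begins (h after start) | Position |
|---|---|---|
| 02:00 | 30–33 | outside |
| 06:00 | 26–29 | outside |
| 10:00 | 22–25 | depends on slot |
| 12:00 | 20–23 | inside |
| 18:00 | 14–17 | inside |
| 22:00 | 10–13 | inside |

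Starts from 00:00 to 08:00 are always outside, and starts from 12:00 to midnight always inside. For 08:00–12:00 starts, with S taken as even over 8–11, 37.5% are outside, 25% straddle and 37.5% are inside.

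**3. Share of patients.** The documents give no start-time distribution, so these are assumed ranges.

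- Even over 24 h: share wholly outside = S/24, from 8/24 = 33% to 11/24 = 46%. Times 36, that is 12 to 16.5, or about 12–17 patients.
- Even over 08:00–20:00: (S − 8)/12, from 0/12 = 0% to 3/12 = 25%, or 0–9 patients.
- If the SAP headings are read as 24 h from the end of a two-hour procedure, the condition becomes T ≤ S − 2. The even-24 h share is then (S − 2)/24, from 25% to 37.5%.

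**4. Possible dilution.** Let f be the share wholly outside and s the share of the 5-point effect that session 2 would add. Neither is in the documents. Difference = 5 × 0.90 × (1 − f·s), SD 4, 18 per arm. Take f = 0.40, close to the 9.5/24 obtained by averaging S over 8–11.

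| s | Difference | Power |
|---|---|---|
| 0 | 4.50 | 91% |
| 0.25 | 4.05 | 84% |
| 0.50 | 3.60 | 75% |

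With f = 0.15 (starts only 08:00–18:00), s = 0.25 and 0.50 give 88% and 86%.

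**5. Follow-up after last use.** Section 6.8 requires at least six days after the last use of the device, while section 6.7 ends participation seven days from the start. In the extreme case session 2 ends 36 h after the start, leaving 168 − 36 = 132 h, or 5.5 days.

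**The case against.** The best defence is that the primary objective concerns the first 24 h and nothing requires that window to contain both sessions. The timing rule is identical in both randomised arms and the endpoint is defined for every patient. Even for inside patients the window is unequally exposed: a noon start in the latest slot leaves no time after session 2. Session times are already recorded (section 6.6) and the device logs use (sections 6.9, 10.5), so timing can be described without altering an endpoint. Only trained research staff operate the device (section 10.8) and their hours are not stated, so night-time enrolment could be rare. Section 6.7 also calls the clock band typical.

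Most of this stands and limits the point. Several stronger readings are tempting but are not supported:

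- *The arms are compared unfairly.* The same rule applies to both, so the effect is at most dilution and blurred meaning.
- *All morning and overnight procedures are affected.* Starts between 20:00 and midnight have session 2 about 8–16 h later, inside the window, and starts from 08:00 to noon depend on the slot.
- *Arrhythmias after a late session 2 are counted nowhere.* The SAP's seven-day outcome contains session 2 for every patient, and its Table 7 lists cardiac arrhythmia as an adverse event. The defect is a 24-hour against seven-day mismatch, with no day-7 data item behind the longer frame.
- *Power is lost.* That depends on assumed values of f and s; if session 2 adds nothing, power stays at 91%.

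Reading the morning after as the same date would put a 02:00 start's session 2 at 6–9 h, inside the window. The Synopsis and Visit 3 contradict that reading.

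**Conclusion.** The conflict is real and bounded. With session 2 on the next calendar morning between 08:00 and 12:00, every start between 00:00 and 08:00 puts it wholly after the protocol's 24 h blood pressure and arrhythmia windows and after the 24 h NIHSS. The affected share is unknown. It is 33–46% if starts are even over the day and 0–25% if they are confined to 08:00–20:00, so zero is possible. The primary comparison remains valid between arms, but it may be diluted and describes a mixture of one-session and two-session exposure. On arrhythmias, the protocol would not count an event after a late session 2, while the SAP would but has no listed item from which to do so. This should be fixed; it does not invalidate the design or the sample size of 36.

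**What to change.** 1. **Arrhythmias.** Reconcile the window in protocol section 2.3.2 and Appendix A with SAP section 3, using one window that contains session 2 for every patient. Add arrhythmias to the day-7 list in section 6.6; a record review at day 7 is already scheduled in section 6.2.
2. **Primary endpoint.** Keep the 24 h coefficient of variation. From the start and end times already collected, derive whether session 2 finished inside the window and report this by arm. Word the conclusion as the effect of session 1, plus session 2 only where it fell inside.
3. **NIHSS.** Report whether the 24 h score came before or after session 2.
4. **Wording.** Reconcile the Synopsis, Visit 3, and sections 6.2, 6.6, 6.7, 6.8 and 10.10 on what the morning after means for post-midnight starts, including the six-day minimum follow-up. Which schedule is right is for the investigators; none is proposed here.

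The cost is protocol and SAP wording, one derived variable and a slightly longer review of routine records. The changes should be settled before allocation is revealed, so that no window is chosen in the light of the results. A supportive coefficient of variation over a longer window is optional. It would not equalise exposure: over about 37 h, a patient starting just after midnight could have about an hour after session 2, and a late-evening starter about a day. It would also lose readings in patients repatriated early.

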#### 6.8 Follow-up procedures

Follow-up is completed seven days after mechanical thrombectomy. The minimum follow-up period following the last use of the investigational device will be six days after the last use of the device, given the performance characteristics, safety and effectiveness of the investigational device. Follow-up will be completed by either reviewing the patient's medical records or calling the patient.

#### 6.9 Compliance

Withdrawal and protocol deviations will be recorded. Non-compliance or missed interventions will be confirmed by the device which records periods of stimulation/activation.

# 7.0 Participant, study, and site discontinuation

It is always within the remit of the responsible clinician to withdraw the participant from the study for appropriate medical reasons. This can be (but is not limited to) individual adverse events, new information gained about a treatment, or if it is felt to be in the participant's best interest. Specific circumstances where participants will be withdrawn from the study are if the auricular stimulation site became inflamed and/or painful.

- If a participant's Personal or Professional consultee wishes to withdraw, data collection and follow-up would continue for withdrawn participants enabling these data to still be used.
- No further blood samples would be collected for withdrawn participants.
- The reasons for participant withdrawal and follow-up information collected would be recorded and timed.
- Participants will not be replaced.
- Withdrawn participants could not be re-entered on this study.
- Clinical data for participants or their representatives that have withdrawn from the study will
  be kept only up until the date they withdrew, unless they also request for their study data to
  be deleted.
- Already collected samples and data would be used [intention-to treat analysis].
- Participants who have become lost to follow-up by seven days will be documented.

#### 8.0 Laboratories and samples

Results from standard of care clinical Barts Health laboratory tests will be recorded. The analysis of troponin measurements will be made from frozen blood samples by The Doctors Laboratory using the Roche high-sensitivity troponin assay

(see: https://labogids.sintmaria.be/sites/default/files/files/troponin\_t\_hs\_2019-02\_v8.pdf) and future research studies.

#### 8.1 Central laboratories

The Doctors Laboratory (vendor, London WC1) for high-sensitivity troponin measurement.

## 8.2 Local laboratories

Results from standard of care clinical Barts Health laboratory tests will be recorded.

#### 8.3 Sample collection, labelling, and logging

All blood samples will be pseudo-anonymised. Samples collected at each participating site will be labelled with the participant's corresponding trial ID and kept in a hospital freezer at an optimal temperature for the troponin assay until collection. The samples will be routinely collected and transferred to WHRI where they will be stored prior to transfer to The Doctor's laboratory. The full sample, collection, labelling, logging and transfer procedure will be documented in the study laboratory log. The trial coordinating team will provide sites with a SOP on sample collection, processing and storage.

#### 8.4 Sample transfer, chain of custody, and accountability

Handling of the samples upon arrival at the local and central laboratory will be documented. All samples will be logged upon receipt and the laboratory will ensure that the physical integrity of these samples have not been compromised in transit. If compromise has occurred, the trial coordinating team, as well as the Sponsor, will be informed of this. Upon receipt of samples, laboratory staff will ensure that all samples are accounted for as per the labelling.

